7.2 Availability

Radiotracer production described in section 2.5

7.3 Acquisition and Accountability

Radiotracer production described in section 2.5

7.4 Formulation, Appearance, Packaging, and Labeling

Radiotracer production described in section 2.5

7.5 Product Storage and Stability

Radiotracer production described in section 2.5

7.6 Preparation

Radiotracer production described in section 2.5

7.7 Dosing and Administration

Radiotracer dose described in section 3.3

7.8 General Concomitant Medication and Supportive Care Guidelines

Not applicable

7.9 Duration of Therapy and Criteria for Removal from Study

Participation in this study is entirely voluntary. Patients may be removed from the protocol for the following reasons:

- Patient decides to withdraw from the study.
- Intercurrent illness that prevents treatment and/or follow-up imaging
- Unacceptable adverse event that may be directly related to the protocol intervention
- General or specific changes in the patient's condition that render the patient unacceptable for further treatment, in the judgment of the investigator
- Does not meet inclusion/exclusion criteria

7.10 Duration of Follow Up

Not applicable.

This is a protocol designed to conform to RDRC regulations and has the specific purpose to study the equivalence of a radiopharmaceutical made using generator and cyclotron produced ⁶⁸Ga. It is not a therapeutic study and therefore does not have end point of treatment outcome.

7.11 Measures to Minimize Bias: Randomization and Blinding

The patients' doses will not be randomized as per FDA guidance documents for bioequivalence -- **21 CFR 320.24(b)** where a crossover design would be plausible, but instead will be conducted in a parallel design since the shipments of Ga-PSMacyc will always be in the afternoon. That said the reader will be blinded as to which of the imaging pair emanated from the Ga-PSMacyc or PSMAGen as the images will be delivered in pairs separate from the imaging sessions. In this way, the rigor of the bioequivalence is retained in the reader/analyst being blinded to the imaging session.

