Exploratory Objectives:	
• Investigate repeatability of whole-body ⁶⁸Ga-PSMA-generator Ki Patlak imaging against that of conventional whole-body ⁶⁸Ga-PSMA- SUV imaging in patients with confirmed metastatic prostate adenocarcinoma.

- Evaluate equivalence of whole-body ⁶⁸Ga-PSMA Ki Patlak imaging between the two processes to create ⁶⁸Ga-HBED-PSMA (⁶⁸GA-PSMA-cyclotron vs. ⁶⁸Ga-PSMA-generator)

Endpoints:

The primary endpoint of this study is to prove equivalence between the cyclotron and generator produced radioisotope. To meet this endpoint we will make a direct comparison of the ⁶⁸GA-PSMA-cyclotron vs. ⁶⁸Ga-PSMA-generator scans obtained within 24-48h. We will measure SUVmean and SUVmax of the same Regions of Interest (ROI) in both scans using the PET analysis software we use in our clinical practice. The two scans will be retrieved and the exact same ROIs will be drawn at the same time for the two scans (software offers a copy-paste function so that no discrepancies exist between the two measurements). The SUVmean and SUVmax obtained from both scans for each Region of Interest will then be analyzed to determine the within-subject coefficient of variation value as measured by the Bland Altman analysis.

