3.1 Overall Design

Thirty patients with metastatic prostate cancer that have undergone standard-of-care staging at WCMC will be considered for enrollment. For this study, enrolled patients will undergo a total of two whole-body dynamic ^{68}Ga -PET scan protocols of at least 0-75 min and at most 0-90 min scan time post injection, depending on the amount of injected dosage. A 6 to 48 hour gap will be introduced between the two scans. The first scan will occur after a baseline clinical evaluation, which will include a history, physical, and baseline lab draw. Blood work will be obtained before, during and after the scan. The radiotracers will be evaluated for repeatability and equivalence across the different production methods. This will include basic pharmacokinetics, distribution, metabolism and excretion.

Up to 30 patients will undergo each two whole-body dynamic scans, initially with ^{68}Ga -PSMAcyc and later with ^{68}Ga -PSMagen (with a minimum time of 6 h and maximum time of 2 days between the two injections). All patients will receive ^{68}Ga -PSMagen from the CBIC core and ^{68}Ga -PSMAcyc from NCM pharmaceuticals at a specific activity of 1-2 Ci/ μmol , the typical specific activity used in published clinical trials with ^{68}Ga -PSMA (10).

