11.2.5 Record Retention

Essential documents are those documents that individually and collectively permit evaluation of the study and quality of the data produced. After completion of the study, all documents and data relating to the study will be kept in an orderly manner by the Investigator in a secure study file. Essential documents should be retained for 2 years after the final marketing approval in an ICH region or for at least 2 years since the discontinuation of clinical development of the IP. In addition, all subjects medical records and other source documentation will be kept for the maximum time permitted by the hospital, institution, or medical practice.

12. Statistical Considerations

Up to 30 patients will undergo a dynamic whole-body scan with ^{68}Ga -PSMA_{Gen} and later ^{68}Ga -PSMA_{cyc} with a maximum time of 2 days and a minimum time of 6 h between the two injections. All 22 patients will receive ^{68}Ga -PSMA_{Gen} at a specific activity of 1-2 Ci/ μmol , the typical specific activity used in clinical trials with ^{68}Ga -PSMA. We expect the ^{68}Ga -PSMA_{cyc} to be delivered and injected at a specific activity of 0.1- 2.0 Ci/ μmol given the rigors of delivery. We will accept doses in this range as the prior small animal imaging was designed to understand the affect of specific activity over a 20X range.

For a power of 80% a calculation of the sample size needed to test odds ratio (equality test) was performed. A sample size of 22 would give a power percentage of 18.47 with a type 1 error of 5%. This power percentage is sufficient in providing confidence that the findings will reflect a true effect. The median statistical power of studies in the neurosciences is between ~8% and ~31%. We will not and should not be focusing on p-values but rather the estimates of the effect size with its confidence intervals.

Estimating repeatabilities using a mixed effects model framework has proven to be powerful, the repeatability (r) is calculated as the variance among group means (group-level variance) over the sum of group-level and data-level (residual) variance (v). A Pearson's correlation coefficient will demonstrate also present the repeatability of results. Intraclass correlation values for both groups will be calculated to test if the groups differ in repeatability. These collection of tests(functions) for estimating repeatability of measurements with a single grouping factor are all performed in R statistical software.

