To quantify the agreement between the two scans, we will use the repeated measures correlation coefficient to account for multiple observations per subject. We will calculate the repeated measures correlation-coefficient for the SUVmax and SUVmean for reference regions as well as regions suspicious for metastatic disease. We will measure SUVmean and SUVmax of the same Regions of Interest (ROI) in both scans using the PET analysis software we use in our clinical practice. The two scans will be retrieved and the exact same ROIs will be drawn at the same time for the two scans (software offers a copy-paste function so that no discrepancies exist between the two measurements). The SUVmean and SUVmax obtained from both scans for each Region of Interest will then be analyzed to determine the within-subject coefficient of variation value as measured by the Bland Altman analysis. If the agreement between the two scans lies within an acceptable rate (which we consider 30% based on previously published data), we will consider the two methods equivalent.

Also, as aforementioned the Bland-Altman Test presents proof of repeatability analysis.

13. Adverse Event Reporting Requirements

Adverse event (AE) monitoring and reporting is a routine part of every clinical trial. The investigator will be required to provide appropriate information concerning any findings that suggest significant hazards, contraindications, side effects, or precautions pertinent to the safe use of the drug or device under investigation. Safety will be monitored by evaluation of adverse events reported by subjects or observed by investigators or research staff, as well as by other investigations such as clinical laboratory tests, x-rays, electrocardiographs, etc.

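### The reader blind in section 7.11 is not shown to hold, and it does not guard against choosing lesions and ROIs that make the two scans agree

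*Combined protocol and SAP*

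**What the plan says.** Protocol section 7.11 states that order will not be randomised, because "the shipments of Ga-PSMacyc will always be in the afternoon". It then relies on the reader not knowing which scan of a pair used which product. The stated mechanism is that "the images will be delivered in pairs separate from the imaging sessions", and the conclusion drawn is "In this way, the rigor of the bioequivalence is retained in the reader/analyst being blinded to the imaging session".

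Scan order is described twice, each time as one fixed order for all patients. Section 3.1 has "Up to 30 patients will undergo each two whole-body dynamic scans, initially with ^{68}Ga -PSMAcyc and later with ^{68}Ga -PSMagen". Section 12 has the reverse: "Up to 30 patients will undergo a dynamic whole-body scan with ^{68}Ga -PSMA_{Gen} and later ^{68}Ga -PSMA_{cyc".

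The Endpoints entry of the Protocol Summary and section 12 describe the reading. Both scans are retrieved and "the exact same ROIs will be drawn at the same time for the two scans", with a copy-paste function to keep the ROIs identical, "using the PET analysis software we use in our clinical practice". Section 12 covers reference regions and regions suspicious for metastatic disease. It declares the methods equivalent if agreement, measured by the within-subject CV from a Bland-Altman analysis, lies within 30%.

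**The concern.** The blind is asked to replace what randomised order would have given. Two things about it look wrong.

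- **It may not conceal the product.** If order is fixed, a reader who sees scan dates and knows the order in use knows the product. Pairing alone hides neither dates nor times.
- **It targets the less important bias.** A product blind protects against favouring one product. Here success means that the two values are close. A reader who wants that result, even without being aware of it, can pick lesions or ROI positions that agree without knowing which scan is which.

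At stake is the primary conclusion. Lesion choice and ROI position are manual, and they feed directly into the CV that is judged against 30%. Bias towards agreement lowers that CV and so favours a finding of equivalence.

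**Working it through.** The plan gives no figure for this point, so there is none to reproduce. Steps 1 and 2 compare the texts; step 3 is an illustration.

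**1. Does the described mechanism conceal the product?**

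- Sections 3.1 and 12 each give a single order, but opposite ones. The documents alone therefore do not tell a reader which scan is which. Scan date plus knowledge of the order actually used does.
- Cyclotron supply is afternoon-only. Time of day identifies the product only if generator scans are not also in the afternoon, and the documents do not say.
- The documents do not mention removal of dates, times or injected activity, coding of scans, random display order, or who holds the key.

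The blind could be made to hold. As written, it is not shown to.

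**2. Would a perfect product blind be enough?**

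No. The endpoint is closeness of two values, and both scans are open when the ROI is drawn. Copy-paste forces one shared ROI, so the reader cannot tune each scan separately. Two choices stay open: which lesions enter, and where the shared ROI sits. No rule for lesion selection or number, or for ROI size, is given. SUVmean is more exposed than SUVmax, which in a discrete lesion depends less on placement.

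**3. How large could it be?**

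The documents give no SUV variance, so every input here is assumed. Let *s* be the SD of log SUV per scan within a lesion and *d* the log difference between scans, normal with mean 0 and variance 2*s*². Then CV = √(exp(mean(*d*²)/2) − 1). The 30% limit is applied to this CV.

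*Start.* With *s* = 0.35, mean(*d*²)/2 = 0.1225 and CV = √(exp(0.1225) − 1) = 36%.

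*Lesion choice.* Leaving out the fraction *f* with the largest |*d*| multiplies mean(*d*²) by v = 1 − 2zφ(z)/(1 − *f*), where z is the 1 − *f*/2 normal quantile.

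| *f* | z | φ(z) | v | 0.1225 × v | CV |
|---|---|---|---|---|---|
| 0 | – | – | 1 | 0.1225 | 36% |
| 5% | 1.960 | 0.0584 | 0.759 | 0.0930 | 31% |
| 10% | 1.645 | 0.1031 | 0.623 | 0.0763 | 28% |

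*Range over which the conclusion changes.* CV = 30% means *s*²v = ln(1.09) = 0.0862. For *f* = 5%, *s*² = 0.0862/0.759 = 0.1136, a true CV of 35%. For *f* = 10%, *s*² = 0.0862/0.623 = 0.1383, a true CV of 38–39%. A true CV above these values still fails, and one below 30% passes anyway.

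*ROI placement.* Simulation with *s* = 0.35 and an added placement error per scan. A correlation between the two scans' placement errors represents how far the shared ROI cancels them. The reader keeps the placement with the smallest |*d*| of three.

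| Placement SD | Correlation | One locked placement | Best of 3 |
|---|---|---|---|
| 0.10 | 0 | 38% | 30% (just above the limit) |
| 0.10 | 0.5 | 37% | 32% |
| 0.10 | 0.8 | 36% | 33% |
| 0.15 | 0 | 40% | 28% |
| 0.15 | 0.5 | 38% | 30% (just below the limit) |
| 0.15 | 0.8 | 37% | 32% |

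The more the shared ROI cancels placement error, the smaller the effect. At a correlation of 0.8 neither case crosses 30%.

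**The case against.** The strongest reply has four parts.

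- **Silence is not evidence of leakage.** Section 7.11 says that the reader will be blinded and that images are delivered apart from the sessions; masking may be intended. This stands. A reader might infer that the blind cannot hold, or that every one of the 30 pairs can be decoded. The documents support neither. They do not say that dates are visible, they contradict themselves on order, and both scans of a pair could fall in the afternoon.
- **The plan has other safeguards.** Copy-paste fixes one ROI for both scans, section 7.1 prefers the same scanner for both, and the same procedures apply to both. This also stands: the blind is not the only protection. None of these governs which lesions enter or where the shared ROI sits.
- **The numbers rest on assumptions.** True. With *s* = 0.25 the CV passes without any selection, apart from the placement-error cases close to 30%; with *s* = 0.45 even the best of five placements fails. The placement model also assumes that the reader can see agreement while drawing, and the plan does not say whether SUVs are displayed. The figures show that the risk is possible, not how large it is here.
- **Drawing on both scans at once limits misregistration.** A fair point, since section 7.1 lets patients leave the couch between passes. It argues for a controlled registration step, not for open choice with both scans in view.

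**Conclusion.** The concern holds in a limited form. The product blind is not shown to hold, because no masking or random display order is described and order is fixed. Even a sound product blind would not address bias towards agreement, which is the reading bias that matters for this endpoint. The claim that blinding preserves rigor is therefore unsupported. No reader blind removes the confounding of product with scan order and, possibly, time of day.

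On assumed inputs (log-SD 0.35 per scan), leaving out the worst-agreeing 5% or 10% of lesions takes the CV from 36% to 31% or 28%. Best-of-3 placement takes 36–40% to 28–33%. The declared result could change only if the true CV lies not far above 30%. It would be wrong to infer that the readings will be steered, or that equivalence would be declared falsely; the documents hold no evidence on either. This should be corrected before any pair is read.

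**What to change.** In sections 7.11 and 12:

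1. Export each scan under a random A/B code once SUV images are computed, with dates and times masked and display order randomised.
2. Prespecify the rule for selecting lesions.
3. Select lesions and draw ROIs on one scan of the pair, picked at random per patient, without displaying the other scan's SUVs.
4. Lock the ROIs and transfer them by copy-paste. Allow only a documented registration correction based on CT anatomy.
5. Extract SUVmean and SUVmax from both scans in one batch, and unblind only after all values are locked.
6. Replace the sentence on rigor with a statement that the reader blind limits reading bias but does not remove the confounding of product with scan order and time of day.
7. Reconcile sections 3.1 and 12 on scan order.

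The cost is a masking step, a random list and a changed reading order, with existing images and staff and no added patient burden. The downside is that the reader cannot adjust an ROI after seeing both values, and residual misregistration may slightly raise the CV.

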7.12 Study Intervention/Follow-up Compliance

Not applicable

8. Study Intervention Discontinuation and Participant Discontinuation/Withdrawal

Participants may withdraw voluntarily from the study. A dedicated Case Report Form (CRF) page should capture the date and the specific underlying reason for discontinuation of study intervention or participant discontinuation/withdrawal.

8.1 Discontinuation of Study Intervention

Not applicable. This is not a therapeutic study.

8.2 Participant Discontinuation/Withdrawal from the Study

This is not a therapeutic study. Participants can withdraw by refusing to perform the scans at any point during the study.

8.3 Lost to Follow Up

A participant will be considered lost to follow-up if we fail to obtain his imaging scan 3 months post-treatment.

The following actions must be taken if a participant fails to return to the clinic for a required study visit:

- The site will attempt to contact the participant and reschedule the missed visit.
- Before a participant is deemed lost to follow-up, the investigator or designee will make every effort to regain contact with the participant (where possible, 3 telephone calls and, if necessary, a certified letter to the participant's last known mailing address or local equivalent methods). These contact attempts should be documented in the participant's medical record or study file.

9. Correlative/Special Studies

Not applicable

10. Measurement of Effect

This is a protocol designed to conform to RDRC regulations and has the specific purpose to study the equivalence of a radiopharmaceutical made using generator and cyclotron produced ^{68}Ga . It is not a therapeutic study and therefore does not have end point of treatment outcome.

10.1 Response Criteria

Not applicable. This is not a therapeutic study.

10.2 Duration of Response

Not applicable. This is not a therapeutic study.

10.3 Progression-Free Survival

Not applicable. This is not a therapeutic study.

10.4 Other Response Parameters

Not applicable. This is not a therapeutic study.

11. Data Reporting / Regulatory Considerations

11.1 Data Collection

The data collection plan for this study is to utilize REDCap to capture all treatment, toxicity, efficacy, and adverse event data for all enrolled subjects.

11.1.1 REDCap

REDCap (Research Electronic Data Capture) is a free data management software system that is fully supported by the Weill-Cornell Medical Center CTSC. It is a tool for the creation of customized, secure data management systems that include Web-based data-entry forms, reporting tools, and a full array of security features including user and group based privileges, authentication using institution LDAP system, with a full audit trail of data manipulation and export procedures. REDCap is maintained on CTSC-owned servers that are backed up nightly and support encrypted (SSL-based) connections. Nationally, the software is developed, enhanced and supported through a multi-institutional consortium led by the Vanderbilt University CTSA.

11.2 Regulatory Considerations

11.2.1 Institutional Review Board/Ethics Committee Approval

As required by local regulations, the Investigator will ensure all legal aspects are covered, and approval of the appropriate regulatory bodies obtained, before study initiation.

Before initiation of the study at each study center, the protocol, the ICF, other written material given to the patients, and any other relevant study documentation will be submitted to the appropriate Ethics Committee. Written approval of the study and all relevant study information must be obtained before the study center can be initiated or the IP is released to the Investigator. Any necessary extensions or renewals of IEC/IRB approval must be obtained for changes to the study, such as amendments to the protocol, the ICF, or other study documentation. The written approval of the IEC/IRB together with the approved ICF must be filed in the study files.

The Investigator will report promptly to the IEC/IRB any new information that may adversely affect the safety of the patients or the conduct of the study. The Investigator will submit written

summaries of the study status to the IEC/IRB as required. On completion of the study, the IEC/IRB will be notified that the study has ended.

Neither the Investigator nor BMS will modify or alter this protocol without the agreement of the other. All agreed protocol amendments will be clearly recorded on a protocol amendment form and will be signed and dated by the original protocol approving signatories. All protocol amendments will be submitted to the relevant institutional IEC/IRB for approval before implementation, as required by local regulations. The only exception will be when the amendment is necessary to eliminate an immediate hazard to the trial participants. In this case, the necessary action will be taken first, with the relevant protocol amendment following shortly thereafter.

Once protocol amendments or consent form modifications are implemented at the lead site, Weill Cornell Medicine, updated documents will be provided to participating sites. Weill Cornell Medicine must approve all consent form changes prior to local IRB submission.

Relevant study documentation will be submitted to the regulatory authorities of the participating countries, according to local/national requirements, for review and approval before the beginning of the study. On completion of the study, the regulatory authorities will be notified that the study has ended.

11.2.2 Ethical Conduct of the Study

The Investigators and all parties involved should conduct this study in adherence to the ethical principles based on the Declaration of Helsinki, GCP, ICH guidelines and the applicable national and local laws and regulatory requirements.

This study will be conducted under a protocol reviewed and approved by the applicable ethics committees and investigations will be undertaken by scientifically and medically qualified persons, where the benefits of the study are in proportion to the risks.

11.2.3 Informed Consent

The investigator or qualified designee must obtain documented consent according to ICH-GCP and local regulations, as applicable, from each potential subject or each subject's legally authorized representative prior to participating in the research study. Subjects who agree to participate will sign the approved informed consent form and will be provided a copy of the signed document.

The initial ICF, any subsequent revised written ICF and any written information provided to the subject must be approved by IRB prior to use. The ICF will adhere to IRB/IEC requirements, applicable laws and regulations.

If consent cannot be obtained in person, written consent can be obtained via a HIPAA-compliant method per the following procedure:

- The participant receives a copy of the informed consent document (e.g., via mail, fax or email) in advance of discussion regarding the study. If mailed, two copies must be mailed. This allows the participant to retain a copy for reference when their signed document is returned to the site. A final copy with all necessary signatures will be sent back to the participant from the site.
- The investigator or designee discusses the study with the potential participant either via telephone or video conferencing. The investigator/designee must have the same consent discussion via telephone/video conferencing that they would have had with the participant during an in-person meeting. The investigator/designee must also implement a method to ensure the identity of the participant (e.g., verification of state identification or other identifying documents or use of personal questions or visual methods). The investigator/designee will also remind the potential participant to conduct this informed consent discussion in a private location to ensure privacy.
- The investigator or designee will provide a comprehensive explanation of the purpose, procedures, and possible risks/benefits of the study in language that is understandable to a non-medically trained person; explain the participant responsibilities and the fact that participation is voluntary; that the participant may withdraw from the study at any time; and that the decision not to participate or to withdraw will not affect the patient's care in any way. The investigator or designee will provide ample opportunity for the participant to ask questions and to consider the decision.
- If the participant expresses a sustained interest, instructions will be given about how the participant needs to sign and date the consent form and how to transmit the signed form back.
- Once the research team receives the signed informed consent document from the participant, the investigator/designee who conducted the consent process must sign and date the document using the current date. Under the signature line, the investigator/designee must document whether consent was obtained over the telephone or video conferencing, the date of the telephone/video conference, and the date the signed consent was received. For example, "Discussed with [participant name] via [telephone or videoconferencing] on [insert date] and received signed consent form on [insert date]." Include a brief reason for performing the informed consent discussion over the telephone/videoconferencing.
- The date the investigator/designee signs the informed consent document, not the date the consent discussion with the participant took place, is the official date of informed consent for the participant on the trial. The informed consent

form is not valid and study enrollment cannot proceed unless all pages are received and appropriately filled out/signed/dated by the participant.

- The final informed consent document must be filed in the designated investigator/site regulatory file location. A copy of the final informed consent document, signed by the participant and the investigator or designee, must be sent back to the participant via email/scan, fax, or postal mail.

